#### Bleeding on Probing (BoP)

Proportion of implants with any bleeding and proportion of bleeding surfaces will be calculated. Analysis of 'any bleeding' over time using the Binomial test will be included.

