#### 6.3.2.4.1 Assessment of periimplant mucosa

PPD and BoP will be evaluated at four surfaces around the implant (mesial, distal, buccal and lingual), by using a periodontal probe. PPD will be measured as the distance from the mucosal margin to the bottom of the probable pocket in mm. Bleeding will be recorded as presence or absence of bleeding when probing to the bottom of the pocket. Plaque will be recorded as presence or absence of plaque by visual inspection on four surfaces at each implant site.

For PPD mean values will be calculated for each implant. Changes over time will be analyzed. The proportion of surfaces that shows presence of bleeding when measuring probing pocket depth will be calculated and presented on an implant level for each visit. Changes over time will be analyzed.

For plaque the proportion of surfaces with presence of plaque will be calculated and presented on an implant level for each visit. Changes over time will be analyzed.

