#### Plaque

Proportion of implants with any plaque and proportion of surfaces with plaque will be calculated. Analysis of 'any plaque' over time using the Binomial test will be included.

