#### Probing Pocket Depth (PPD)

The measured aspects/sides as well as implant mean value will be presented and used in analysis. Descriptive statistics for absolute values and the change from baseline (Visit 5; Permanent Restoration) will be calculated. Analysis over time using the Wilcoxon Signed Rank test will be included.

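### Section 6.3.2.4.1 promises an analysis of change in the proportion of bleeding and plaque surfaces, but 10.3.2 names an over-time test only for any versus none, which cannot register worsening in an implant already affected

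*Combined protocol and SAP*

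**What the plan says.** The measurement scale is set in section 6.3.2.4.1. For bleeding: "PPD and BoP will be evaluated at four surfaces around the implant (mesial, distal, buccal and lingual), by using a periodontal probe". For plaque: "Plaque will be recorded as presence or absence of plaque by visual inspection on four surfaces at each implant site". Each implant therefore has 0 to 4 affected surfaces at each visit.

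The same section defines the variable to be followed, visit by visit. For bleeding: "The proportion of surfaces that shows presence of bleeding when measuring probing pocket depth will be calculated and presented on an implant level". The plaque definition runs in parallel: "For plaque the proportion of surfaces with presence of plaque will be calculated and presented on an implant level for each visit". After each definition it adds that changes over time will be analysed.

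Section 10.3.2 opens the peri-implant mucosa objective with a general promise of descriptive statistics and an analysis over time, naming neither variable nor method. Under bleeding and under plaque it calculates both the proportion of implants with any affected surface and the proportion of affected surfaces. The named tests are: "Analysis of 'any bleeding' over time using the Binomial test will be included" and "Analysis of 'any plaque' over time using the Binomial test will be included".

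Probing pocket depth is measured at the same four surfaces. It keeps its scale, uses Visit 5 as baseline, and gets a different test: "Analysis over time using the Wilcoxon Signed Rank test will be included".

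**The concern.** Section 6 says change in a five-level measure will be analysed, while section 10 names a test only for its two-level collapse. One affected surface out of four is enough to make an implant positive. From then on the named test can record only no change or improvement; spread from one surface to four is a tie.

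The secondary objective is the condition of the peri-implant mucosa up to five years. As affected implants become common, the any/none measure saturates. A non-significant test could then stand in the report beside a rising proportion of affected surfaces, with no planned test of that rise. A method for it chosen after the data are seen would be post hoc. Section 10.1 says only that a separate SAP may be prepared, so nothing in the documents guarantees that the gap will be closed in time.

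**Working it through.** **1. The plan's own figure.** The documents give no rates, effect size or power for bleeding or plaque. The only sample-size figure, in section 10.4, is for the primary endpoint. It reproduces: n = [(1.9600 × √(0.90 × 0.10) + 1.2816 × √(0.97 × 0.03)) / 0.07]² = 132.8, rounded up to 133. Then 133/0.85 = 156.5, rounded up to 157. The 133 serves below only as a realistic number of implants.

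**2. What the named test can see.** On a 0-4 scale there are 5 × 4 = 20 possible non-zero changes, of which 10 are worsenings. Any/none changes only when one end is 0, so the four worsenings from 0 are seen. The other six are ties: 1→2, 1→3, 1→4, 2→3, 2→4 and 3→4. Of all 20 changes, 12 are ties. This needs no assumption about rates.

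**3. A constructed example.** Take 133 implants, of which 50 have one bleeding surface at baseline and 83 have none. Let 30 of the 50 go to four surfaces and the rest stay the same.

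- Any bleeding: 50/133 = 37.6% at both visits, with no discordant pairs, so the binomial test has nothing to test.
- Bleeding surfaces: 50/(4 × 133) = 9.4% at baseline. At follow-up, (20 × 1 + 30 × 4)/(4 × 133) = 140/532 = 26.3%.
- Wilcoxon signed-rank test on the within-implant change in count: p = 4 × 10⁻⁸.

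**4. Power when both measures move.** All inputs here are assumptions: 120 paired subjects, two-sided 5%, and four correlated surfaces from a latent normal model with subject correlation 0.2 and visit correlation 0.2 to 0.4. The plan's binomial test over time is read as an exact test on discordant any/none pairs. It is compared with the Wilcoxon signed-rank test on the count.

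| Affected surfaces | Any/none | Surface count |
|---|---|---|
| 30% to 40% | 46-49% | 68-82% |
| 40% to 50% | 33-38% | 63-78% |
| 15% to 22% | 47-51% | 59-69% |
| 10% to 15% | 36-42% | 46-55% |
| 5% to 10% | 54-64% | 63-76% |
| 5% to 8% | 24-29% | 31-39% |

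With stronger clustering of surfaces within a visit (0.6), 15% to 22% gives 38% versus 45%. With no true change, rejection was 4.5-5.5% for the count and 2.8-4.1% for any/none in one set of runs, and about 3-6% in a repeat. The count's advantage is therefore not bought with a materially inflated error rate.

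**5. The blind spot alone.** With 133 implants and visits drawn independently, the share with any affected surface is held at 30%, 50% or 70% at both visits while the extent worsens. Among affected implants the baseline split over 1/2/3/4 surfaces is 70/20/5/5%.

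- Follow-up split 20/20/30/30%: any/none rejects in 3-4% of runs; the count test rejects in 80%, 98% and 100%.
- Follow-up split 40/30/20/10%: 3-4% versus 30%, 54% and 83%.

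This set-up favours the count by construction. It shows what the named test misses, not what is likely to happen.

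**6. Reference visit.** Section 5.1.5 and Appendix B record bleeding and pocket depth at Visit 5 but not plaque. Plaque first appears at Visit 6. Pocket depth's Visit 5 baseline can be carried over to bleeding but not to plaque.

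**The case against.** The best reply is that nothing is hidden. Section 10.3.2 requires the proportion of affected surfaces to be calculated, 6.3.2.4.1 requires it per implant at each visit, and sections 10.1 and 10.3 call for descriptive statistics on every variable, with confidence intervals where appropriate. A reader might infer that spread from one surface to four would go unreported. The documents do not support that: it would be a tie in the named test but visible in the tables.

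A reader might also infer that the two sections flatly contradict each other. They do not. The general promise of analysis over time, and the wording that the binomial test will be included, leave room for a further test. The fault is a mismatch: section 6 promises an analysis for which section 10 names no method, while section 10 attaches its only named test to a coarser measure.

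Any bleeding per implant is also a legitimate and easily understood summary, and section 2.2 lists the outcomes without fixing a scale. Nothing requires it to be dropped.

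Finally, a large power loss depends on assumed high prevalence, plaque was not simulated separately, and these outcomes carry no success criterion. All of that stands, and it limits the size of the point. It does not remove it: the count test did better in every non-null scenario run, and the plan gives no reason for treating bleeding and plaque differently from pocket depth.

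**Conclusion.** The point holds as a cheap improvement to a secondary analysis. That 6 of 10 worsenings are ties follows from the scale alone. The size of the power gain rests on assumed rates and correlations: about 5-15 points at low prevalence or with strong within-visit clustering, and about 15-40 points when 30-50% of surfaces are affected. The primary endpoint, the sample size and the safety analysis are untouched. It would go too far to conclude that mucosal deterioration will be missed or that the any/none analysis is invalid.

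**What to change.** In section 10.3.2:

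- Make the Wilcoxon signed-rank test on within-implant change in the number (equivalently, proportion) of affected surfaces the main over-time test for bleeding and for plaque.
- For bleeding, state Visit 5 as the reference.
- For plaque, state the reference visit explicitly. The first available is Visit 6, since plaque is not recorded at Visit 5.
- Keep any bleeding and any plaque as supplementary summaries, with or without the binomial test.

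This gives the change analysis promised in 6.3.2.4.1 a named method. The cost is a few sentences. The surface-level data are already collected and the test is already in the plan for pocket depth. The downside is one more test to report if the binomial test is kept, and a main measure that is less simple to explain than any versus none.

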#### Plaque

Proportion of implants with any plaque and proportion of surfaces with plaque will be calculated. Analysis of 'any plaque' over time using the Binomial test will be included.

#### Probing Pocket Depth (PPD)

The measured aspects/sides as well as implant mean value will be presented and used in analysis. Descriptive statistics for absolute values and the change from baseline (Visit 5; Permanent Restoration) will be calculated. Analysis over time using the Wilcoxon Signed Rank test will be included.

### 10.3.3 Safety analysis

All safety variables will be summarized by means of descriptive statistics. No hypotheses will be tested.

# 10.4 Determination of sample size

In this study, subjects will receive single crown restorations and the primary objective is prosthetic survival one year after permanent restoration. Studies reporting on implant-supported single crowns found in the literature  $^{17-20}$ , show a prosthetic survival rate of 96.3% (95% CI: 94.2–97.6%) after 5 years. Following this, the expected true prosthetic survival rate, after one year, is set to 97% (= $\pi$ 1).

The aim is to estimate the proportion of subjects with "success". The hypotheses of interest are

 $H_0$ :  $\pi$  ≤  $\pi_0$  and  $H_1$ :  $\pi$  >  $\pi_0$ 

Limit to be tested against H0: 90 %. The null hypothesis will be rejected if the two-sided p-value is less than  $\alpha$  = 0.025 and if  $\pi$  =  $\pi$ 1 (97%) the power to reject H0 should be 90 %.

The formula to calculate the sample size is (n is the number of fully evaluable subjects)

$$n = \left[ \frac{\lambda_{\alpha} \sqrt{\pi_0 (1 - \pi_0)} + \lambda_{1 - \beta} \sqrt{\pi_1 (1 - \pi_1)}}{\pi_0 - \pi_1} \right]^2$$

In the formula  $\lambda_x$  is the x:th quintile of the standardized normal distribution.

As it is a one-sided hypothesis:

$$\alpha$$
 = 2.5 %  $\lambda_{\alpha}$ = 1.9600  $\beta$  = 90 % then  $\lambda_{1\text{-0.90}}$  0 1.2816.

Given the assumptions above the sample size is estimated to include 133 evaluable subjects with a power of approximately 90 %.

Assuming a subject drop-out rate of 15 % a total of 157 (=133/0.85) is expected to be included in the study.

### 10.5 Statistical analysis during the course of the study

Partial clean file will be declared when all subjects have completed:

- Visit 7 (1-year follow-up after PR) data will be used for 1-year follow-up publication.
- Visit 9 (3-year follow-up after PR) data will be used for 3-year follow-up publication.

Additional partial clean files may be performed when all subjects have completed:

Visit 5 (Permanent Restoration) – Demographic and Baseline data

Data base lock will take place and total clean file will be declared when all subjects have completed:

Visit 11 (5-year follow-up) – data will be used for 5-year follow-up publication.

### List of abbreviations

ADE Adverse Device Effect

AE Adverse Event

CDMS Clinical Data Management System

CIP Clinical Investigation Plan

CRF Case Report Form
DBL Database Lock

DCF Data Clarification Form
DD Device Deficiency
DMP Data Management Plan
EDC Electronic Data Capture
EMA European Medicines Agency
FDA Food and Drug Administration

FSI First Subject In

IB Investigator's Brochure ICF Informed Consent Form

IEC Independent Ethics Committee

IFU Instructions For Use
IP Investigational Product
IRB Institutional Review Board
ISF Investigator Site File
LSI Last Subject In

LSI Last Subject In LSO Last Subject Out

PMDA Pharmaceuticals and Medical Devices Agency

PP Per Protocol

RA Regulatory Authorities SAE Serious Adverse Event

SADE Serious Adverse Device Effect

SDV Source Data Verification

USADE Unanticipated Serious Adverse Device Events

USAE Unanticipated Serious Adverse Events

# Appendix B: Visit and procedure plan

Visit name	Screening and pre-surgical planning	Implant Placement (IP)	Post-op (PO)	Impression	Permanent Restoration (PR)	Follow-up
Visit number	1	2	3	4	5	6-11
Visit window			IP + 1-2 weeks	IP + max 5 ½ months	IP + max 6 months	PR + 6 months, 1, 2, 3, 4, 5 years (± 1 month)
Written Informed Consent	X					
Inclusion/Exclusion criteria	Χ	Χ			Χ	
Subject demographics	Χ					
Medical/Surgical history	X					
Oral examination	Χ					
Radiographic examination	X 	Χ			Χ	X 
Clinical photography 	Χ	Χ		Χ	Χ	X 
Implant stability		Χ		Χ	Χ	
Condition of periimplant mucosa (BoP, PPD)					Χ	Χ
Plaque						Χ
Adverse Event documentation		Χ	Χ	Χ	Χ	Χ

[figure not shown]
 If pre-existing radiographs are insufficient or older than 6 months

 Clinical photographs will be taken for at least 5 subjects selected by each study site

 X-rays and clinical photographs will be taken at 1, 3 and 5 year follow-up (visit 7, 9 and 11)

# Appendix C: Dental chart

[figure not shown]
The two-digit-notation system as standardized by the Fédéderation Dentaire Internationale (F.D.I.) is used for the documentation.

Upper				Lower				
F	Right		Left Left		Left		Right	
FDI	Universal	FDI	Universal	FDI	Universal	FDI	Universal	
11	8	21	9	31	24	41	25	
12	7	22	10	32	23	42	26	
13	6	23	11	33	22	43	27	
14	5	24	12	34	21	44	28	
15	4	25	13	35	20	45	29	
16	3	26	14	36	19	46	30	
17	2	27	15	37	18	47	31	
18	1	28	16	38	17	48	32	

[figure not shown]
# Appendix D: Overview – Types of safety events

Safety events involving subjects:

\*SAE and SADE must be promptly reported in the eCRF by the Investigator

Safety events associated with the product itself, not with the subject:

\*\*DD with SADE potential must be promptly reported in the eCRF by the Investigator
